1.0 Background & Rationale

Parents faced with surgical decisions for their children encounter irreversible choices with potentially lifelong consequences. They must balance tradeoffs between disease outcomes, surgical treatment success, and side effects given that no single management strategy will achieve all of a patient's or parent's goals. Therefore, decisional conflict may arise, manifesting itself through patients' or parents' verbalizing uncertainty, expressing concerns about outcomes, wavering between choices, delaying decisions, questioning their personal values, being preoccupied with the decision, or expressing emotional distress.¹ To date, few studies have examined parental decision-making for pediatric surgery or decisional conflict/regret regarding these decisions.²⁻⁶ The objective of this 5-year project is to use a multi-modal approach to develop a decision aid that will deliver clear, accurate parent-informed material about hypospadias. The goals of this research are to empower parents to make informed decisions about surgery for their children and improve their level of satisfaction with the decision afterwards. The central hypothesis is that decision aids developed using parent-centered research strategies can successfully reduce decisional conflict by better informing the surgical decision-making process.

2.0 Research Aims

AIM 1 (Year 1): Utilize patient-centered design research methods to explore: a) the parental decision making process regarding hypospadias repair, including identifying parental attitudes, perceptions, and informational needs, and b) outcomes of importance to parents of children with hypospadias.

AIM 2 (Year 2): Assess qualitatively providers' attitudes about shared decision-making and use of a decision aid (DA) for hypospadias, including feasibility and utilization in the context of a clinic visit.

AIM 3 (Years 3 and 4): Create a decision aid and postoperative outcome measurement tool for use by parents facing decisions regarding hypospadias repair and by those who have elected repair, respectively, based on the factors identified in Aims 1 and 2 of the study.

AIM 4 (Years 4 and 5): Conduct a pilot field test (pre-test/post-test) of the decision aid in the clinical setting and conduct a preliminary psychometric assessment of the patient-centered outcome measurement tool.

3.0 Pilot Testing Objectives

The primary purpose of the pilot field test is to determine the feasibility and acceptability of implementing the decision aid (DA) in the clinical setting and to measure its efficacy for our key outcomes. To determine feasibility, our primary outcomes are: (1) percent of eligible parents screened; (2) percent of eligible parents enrolled, and (3) percent of parents retained in the study. To determine acceptability, our primary outcome is to assess the DA's content, length,

clarity, and balance of information. Our secondary outcomes include knowledge of treatment options, knowledge of hypospadias, choice predisposition, decisional conflict, decisional regret, shared decision making, and preparation for decision making. We will also qualitatively examine urologists' views about the DA's applicability in their practice context, DA's perceived efficacy in assisting parents to arrive at a treatment-related decision, and perceived barriers and facilitators to DA implementation.

4.0 Criteria

4.1 Inclusion Criteria

Parents: 18 years of age and older of sons (ages up to 5 years) with hypospadias, or a tentative hypospadias diagnosis and/or referral to urology for hypospadias and are planning to attend the urology appointment; able to consent and do interview in English; aware that there is an issue with the child's pee hole; and, have access to a reliable internet and smart phone, tablet, or computer to view the website (DA). The child/patient will be scheduled to see a urologist but must not have seen the urologist at the time of enrollment. (Parents ideally have not yet made a final decision about surgery at the time of enrollment.)

To assure representation in our parent sample, we will attempt to recruit samples that include mothers, fathers, diversity in patient/parent race and ethnicity, education/socioeconomic status, health literacy and possibly device used to access the website (e.g. computer, phone).

Providers: general pediatrician or general pediatric nurse practitioner; pediatric urologist or pediatric urology nurse practitioner.

4.2 Exclusion Criteria

Parent Pilot Testing: If, during the recruitment call the parent states they are not aware of any issue with the child's pee hole, not simply unaware of the term hypospadias, then the parent would be excluded. If, at the clinic visit, the urologist decides that the patient does not have hypospadias, then the parent will be notified that she/he will be withdrawn from the remaining data collection points as they are no longer in a decision-making process about surgery. If we fill target groups (to balance parents' gender, race, or ethnicity), we may exclude some parents in order to have a balanced sample.

For all potential participants (except providers), the PI may use discretion if a medical (or other) condition makes a patient or parent inappropriate to enroll in a study activity.

All participants: Non-English speaking or illiterate. All activities will require a discussion and/or completion of written activities that require English competency.

5.0 Study Design

We will use a multi-modal, parent-centered approach to develop a decision aid that will deliver clear, accurate parent-informed material about distal hypospadias surgery. The decision aid will undergo three sets of testing and iterative re-designs. The study's current phase, pilot testing, involves field testing of the website by parents of boys with hypospadias and by providers (e.g. pediatric urologists).

6.0 Enrollment

6.1 Parents/Patients

We will identify new patients via urology clinic schedules (patients diagnosed with hypospadias and/or received a referral for hypospadias). Providers may also refer patients and parents to the research team. Recruitment of parents for pilot testing will take place via a phone with caller ID, in person/in the clinic, U.S. mail, email, and/or text message. First, a well-trained research assistant will introduce him/herself. For example, "I am a research assistant working with [name] who is a pediatric urologist at UNC Chapel Hill. I am located at IU School of Medicine and we are partnering with her team at UNC on this research. I'm calling to invite you to review a tool to help parents and physicians make decisions about surgery." If the parent expresses interest, the RA will then review the study procedures and goals with parents verbally in person, over the phone and/or by text. Over the phone, the research assistant will offer to send a copy of the consent documents via email. Parents will have the opportunity to ask questions and further consider participation. Those who choose to enroll will provide verbal consent, which will be documented by the research assistant in the REDCap database (on a secure departmental server).

6.2 Providers

Medical providers (including pediatric urologists, general pediatricians or general pediatric nurse practitioners, pediatric urologists or pediatric urology nurse practitioners) will be invited to participate via email, in person, or over the phone. A research assistant will present and explain the Study Information Sheet to the provider. Then, the provider will have the opportunity to ask questions and further consider participation. Those who choose to enroll will provide verbal consent, which will be documented by the research assistant in the REDCap database.

7.0 Study Procedures

7.1 Parent Pilot Testing of Decision Aid

Research assistants will collect data from parents at four time points, twice before and twice after their son's first visit with a pediatric urologist/pediatric urology nurse practitioner for a potential or actual diagnosis of hypospadias. The questions will address website usability,

feedback on content, usefulness in decision-making, and basic demographic questions. Data will be collected via phone interview with a research assistant. Interviews may be recorded and professionally transcribed for analysis. Reminders will be sent to parents between the four time points regarding looking at the website and the upcoming data collection calls. We anticipate that each data collection point will require 10-30 minutes for parents to complete. We will also use a website plug-in to track any analyze how parents move through the website. We plan to interview 10-25, but no more than 40 parents (n=40) who complete all timepoints of the study.

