8.0 Study Calendar

Parent Pilot Test Data Collection Schedule	
Baseline (T1)	
 • Demographics/Health Literacy (8 questions) • Decisional Conflict Scale (DCS) (16 questions) • Decision-Specific Knowledge Test (6 questions) • Treatment Preference/Awareness of Decision (2 questions) 
Recommendation: Have any of your child’s healthcare providers already made a recommendation about your son’s hypospadias? If so, what was the recommendation? (1 question)

Pre-consultation, 1 week after baseline (T2)	
 • Website Viewed (3 questions) 
 ○ Did you have time to look at the website ○ Did you view the website with anyone else? ○ Did you view the website on a smart phone, tablet, or computer? • Treatment Preference/Awareness of Decision (2 questions) • Decisional Conflict Scale (DCS) (16 questions) • Decision-Specific Knowledge (6 questions)

	
 • Decision Aid Acceptability Questionnaire (4 questions) • Preparation for Decision Making Scale (10 questions)
Initial post-consultation, within 48 hours of urology visit (T3)	
 • Treatment Preference/Awareness of Decision (2 questions) • Decisional Conflict Scale (DCS) (16 questions) • Shared Decision Making Questionnaire (SDM-Q-9) (9 questions) • Preparation for Decision Making Scale (PrepDM) (10 questions) • Open-ended questions (3 questions) 
 ○ What most impacted your decision during/after your visit with the urologist? ○ How did you use the decision aid during your visit with the urologist? ○ Is there anything we didn't cover that you would like to share?
3-month post-consultation (T4)	
 • Decision Regret Scale (5 questions) • Open-ended questions (2 questions) 
 ○ What do you wish you would've known when you were making the decision? ○ Is there anything that we didn't cover that you would like to share?

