13.0 Statistical Data Management

Primary data for surveys and interviews will be collected, managed, and stored electronically in REDCap and/or the secure department server. During data collection, any questions or concerns will be flagged in the REDCap database for PI review. Additional quality assurance steps will include: testing of database by study team prior to moving to production mode and extraction and cleaning of data that will be used for analysis every two months.

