17.0 Appendix

To assess the quality of the decision-making process and the impact of the decision aid, we will utilize these scales:

- **Decisional Conflict Scale (DCS).** DCS is a validated scale that has been extensively studied and consists of 10 statements and 5 response categories ranging between 0 (no decisional conflict) and 100 (extremely high decisional conflict).
- **Decision-Specific Knowledge.** We used data from Aims 1 and 2 to inform the development of a questionnaire to determine decision-specific knowledge of hypospadias treatment options/outcomes. We decided a priori that a score of 80% must be attained on this questionnaire as an indicator of being “informed.”
- **Hypospadias Treatment Preference/Awareness of Decision.** Parents will be asked whether they intend to have their child undergo hypospadias surgical repair and whether they are aware that there is a decision to be made.
- **Decision Aid Acceptability Questionnaire.** We will also assess the acceptability of the DA using a tool similar to the Decision Aid Acceptability Questionnaire. Questions will elicit feedback on amount of content, clarity, and helpfulness of the DA, acceptability of format and whether the information was presented in a balanced and fair manner.
- **Preparation for Decision Making Scale (PrepDM).** This 10-item scale assesses a patient's perception of how useful a decision aid is in preparing the respondent to communicate with their practitioner at a consultation focused on making a health decision.
- **Shared Decision Making Questionnaire (SDM-Q-9):** This is a 9-item self-report instrument developed to measure the process of SDM as perceived by the patient. The scale has high internal consistency, high item discriminations, and showed high face and factorial validity.
- **Decision Regret Scale:** The Decision Regret Scale measures distress or remorse after a health care decision. We will perform an early assessment of DR in this study with plans to re-assess the long-term level of regret in a future randomized controlled trial.

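### Acceptability, a primary outcome, is rated once and only aloud to a project research assistant, so the ratings are at risk of favourable courtesy bias that nothing else in the plan measures or corrects

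*Combined protocol and SAP*

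**What the plan says.** - **Status.** Section 3.0 names the outcome: "To determine acceptability, our primary outcome is to assess" the aid's content, length, clarity and balance. Three feasibility percentages are also primary.
- **Instrument.** Section 8.0 lists "Decision Aid Acceptability Questionnaire (4 questions") at T2 and at no other time point. The Appendix (17.0) says the tool covers, among other things, "whether the information was presented in a balanced and fair manner".
- **Timing.** T2 is labelled "Pre-consultation, 1 week after baseline (T2"). Section 11.0 withdraws a parent whose T2 data are not collected before the visit. The interval from T2 to the visit is not given.
- **Mode.** Section 7.1: "Data will be collected via phone interview with a research assistant". The same section allows the calls to be recorded.
- **Setting.** In Section 6.1 the example recruitment script presents the assistant as working with a pediatric urologist and partnering with that urologist's team, and then says the call is to "invite you to review a tool to help parents and physicians make decisions about surgery". Aim 3 in Section 2.0 shows that the same project creates the aid. Section 7.2 has the provider told that the parent has consented.
- **Means already in place.** Section 4.1 requires that parents "have access to a reliable internet and smart phone, tablet, or computer to view the website (DA"). Section 4.2 excludes people who are illiterate or do not speak English and foresees written activities. Section 6.1 uses email and text for contact. Section 13.0 states: "Primary data for surveys and interviews will be collected, managed, and stored electronically in REDCap and/or the secure department server".

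**The concern.** A parent who has not yet met the urologist is asked, by name and by voice, to judge a tool introduced in connection with a urologist's team. People tend to soften criticism in that setting, and the plausible direction is favourable. Balance is the most exposed item, because rating it low amounts to telling the project that its material leans one way.

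Acceptability is one of the main results the pilot will report, and it is measured once in one mode. If the answers are softened, nothing collected elsewhere would show it. The result could then be carried into the larger trial that Section 12.0 has in view as firmer support for the aid than parents privately hold.

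**Working it through.** **1. No plan figure to reproduce.** The documents state no acceptability threshold, expected rate, power or precision. Section 12.0 provides descriptive statistics only. All rates below are assumptions.

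**2. Could anything else in the plan detect or correct softened ratings?**

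| Provision | Why it does not help |
|---|---|
| Right to skip questions (14.0) | Allows silence; does not measure candour |
| Website tracking (7.1) | Shows navigation, not opinion on clarity or balance |
| PrepDM at T2 and T3 (8.0) | A different construct, also collected by phone |
| Open-ended questions (8.0) | Only at T3 and T4, by phone; qualitative results are ranked tertiary (12.0) |
| Provider interviews (7.2) | Providers' views, not parents' ratings |

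No self-completed option, independent interviewer or neutral script is described.

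**3. Size of a possible shift.** Let p be the share of parents who would privately rate the aid favourably, and s the share of the remainder who soften their answer. Reported share = p + (1 - p) x s. With p = 0.70:

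- s = 0.20: 0.70 + 0.30 x 0.20 = 0.76
- s = 1/3: 0.70 + 0.30 x 1/3 = 0.80
- s = 0.50: 0.70 + 0.30 x 0.50 = 0.85

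The 6 to 15 point shift follows entirely from the assumed inputs and is not an estimate.

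**4. Shift against sampling error.** Section 7.1 plans 10-25 parents and at most 40. Exact (Clopper-Pearson) 95% intervals for an observed 80% are:

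- 8/10: 44% to 98%
- 20/25: 59% to 93%
- 32/40: 64% to 91%

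Now assume a true rate of 70%, a 10-point reporting shift, and 80% as the level a reader would call acceptable. The chance of seeing at least 80% favourable is the binomial tail P(X >= 0.8n), with success probability 0.70 (no shift) or 0.80 (shift). Coverage is the chance that the exact 95% interval contains the true 70%.

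| n | P(at least 80%), no shift | P(at least 80%), +10 points | Coverage of 70%, +10 points |
|---|---|---|---|
| 10 | 38% | 68% | 99.9% |
| 25 | 19% | 62% | 90% |
| 40 | 11% | 59% | 71% |

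At n = 10 the interval is so wide that sampling error dominates. Towards n = 40 the interval narrows but the shift does not, so the shift increasingly decides what is concluded.

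**The case against.** The strongest case for the phone is the sample. Section 4.1 deliberately seeks variety in education and health literacy, and reading questions aloud helps parents who find forms hard. Calls also limit missing data: with 10-25 parents, two unfinished links would cost 2/25 = 8% to 2/10 = 20% of a primary outcome. Rating before the visit keeps opinions of the aid separate from the consultation. No threshold or go/no-go rule is attached to acceptability, so no stated decision turns on a shift of a few points. Choosing an interviewer over a form contradicts nothing in the plan.

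Most of this stands. It argues for keeping the phone available and leaving the timing alone. It does not argue for the phone as the only mode for four short items, and the absence of a threshold does not make a softened primary result harmless to report.

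Some stronger readings are tempting, but the documents do not support them:

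- *The interviewers built the aid.* The Section 6.1 script is an example for recruitment, not for the T2 call. It does not say who made the tool, and it places the assistant at a different institution from the urologist. Only the project's authorship of the aid is documented.
- *T2 falls immediately before the visit.* The plan says only one week after baseline and before the consultation.
- *A second arm would have cancelled the bias.* Parents not given the aid could not rate it, so the single-group design is not the cause.
- *Every eligible parent could self-complete.* The device requirement is for viewing the website, and Section 13.0 does not say that parents enter data in REDCap themselves. Feasibility is a reasonable inference for most parents.

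**Conclusion.** The point holds as a risk to a primary outcome, and the remedy is cheap. The documents establish the primary status, the single measurement before the visit, the oral mode, and the lack of any other check on candour. They do not show that bias occurs. A reader might infer that the ratings will be biased upward by a known amount, but upward is only the plausible direction and the size is unknown. The 76% to 85% range and the probabilities above rest on an assumed 70% true rate, assumed softening shares or a 10-point shift, and an 80% benchmark that the plan does not set.

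The point also assumes that the four questions are mainly closed ratings, since their response format is not given. It does not extend to the open-ended questions, for which an interviewer is a natural choice. This is a recommended improvement to how one outcome is collected, not an error in the analysis.

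**What to change.** In Section 7.1, with a matching note in Section 8.0:

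1. At T2, and before the visit, send each parent a REDCap link by text or email to the four acceptability items. The parent completes it off the call, or at least without the assistant seeing the answers.
2. Tell parents that their urologist will not see individual ratings, and set data access so that this is true.
3. Keep the phone as a fallback for parents who do not complete the link or prefer to answer aloud. Record the mode for each parent.
4. Report acceptability overall and by mode, descriptively. The numbers by mode will be too small for a formal comparison.
5. Leave the Decisional Conflict Scale and the knowledge test by phone, so that the pre/post comparisons in Section 12.0 are not confounded with a change of mode. PrepDM may move to the link, but only if T2 and T3 use the same mode.

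The cost is one short form and a minor amendment. The downside is a few unfinished links and some mixing of modes in a planned 10-25 parents; the phone fallback limits the missing data. Self-completion reduces the pressure to be polite but does not make answers anonymous to the study team. If the mode is left as it is, the report should state the limitation beside the acceptability result.

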7.2 Post-Pilot Testing and Debriefing with Providers

Urology providers permission to approach their individual patients will be requested on a rolling basis during the enrollment portion of the study. If the provider allows approach, and consent is given, the provider will be notified their patient’s parent has consented and will be reminded of the upcoming consented patient appointment. Research assistants and/or the PI will conduct interviews with urology providers. Interviews will occur after a provider has interacted with parent participants at their child’s clinic visit for hypospadias. We will assess the providers’ views of the applicability of the decision aid in the practice context, perceived efficacy of the tool in assisting parents to arrive at a treatment-related decision, and perceived facilitators to decision aid implementation. We will also collect any feedback on the content and layout of the decision aid website. We anticipate that interviews will be 10-30 minutes long and may be recorded and professionally transcribed for analysis. We will also use a website plug-in to track and analyze how providers move through the website. We plan to interview 5-10 providers.

8.0 Study Calendar

Parent Pilot Test Data Collection Schedule	
Baseline (T1)	
 • Demographics/Health Literacy (8 questions) • Decisional Conflict Scale (DCS) (16 questions) • Decision-Specific Knowledge Test (6 questions) • Treatment Preference/Awareness of Decision (2 questions) 
Recommendation: Have any of your child’s healthcare providers already made a recommendation about your son’s hypospadias? If so, what was the recommendation? (1 question)

Pre-consultation, 1 week after baseline (T2)	
 • Website Viewed (3 questions) 
 ○ Did you have time to look at the website ○ Did you view the website with anyone else? ○ Did you view the website on a smart phone, tablet, or computer? • Treatment Preference/Awareness of Decision (2 questions) • Decisional Conflict Scale (DCS) (16 questions) • Decision-Specific Knowledge (6 questions)

	
 • Decision Aid Acceptability Questionnaire (4 questions) • Preparation for Decision Making Scale (10 questions)
Initial post-consultation, within 48 hours of urology visit (T3)	
 • Treatment Preference/Awareness of Decision (2 questions) • Decisional Conflict Scale (DCS) (16 questions) • Shared Decision Making Questionnaire (SDM-Q-9) (9 questions) • Preparation for Decision Making Scale (PrepDM) (10 questions) • Open-ended questions (3 questions) 
 ○ What most impacted your decision during/after your visit with the urologist? ○ How did you use the decision aid during your visit with the urologist? ○ Is there anything we didn't cover that you would like to share?
3-month post-consultation (T4)	
 • Decision Regret Scale (5 questions) • Open-ended questions (2 questions) 
 ○ What do you wish you would've known when you were making the decision? ○ Is there anything that we didn't cover that you would like to share?

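### Viewing of the decision aid and its acceptability are scheduled only at T2, so a parent who first opens the site between T2 and the visit never gives an acceptability rating

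*Combined protocol and SAP*

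**What the plan says.** Section 3.0 makes acceptability primary: "To determine acceptability, our primary outcome is to assess the DA's content, length", with clarity and balance completing the list.

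The Study Calendar (Section 8.0) places the four-question acceptability questionnaire at T2, one week after baseline and before the consultation. It does not appear at T1, T3 or T4. The three website-viewing questions are also at T2 only, and the first is "Did you have time to look at the website". T3, within 48 hours of the urology visit, repeats PrepDM and asks an open-ended question, "How did you use the decision aid during your visit with the urologist". It contains no question on whether the parent has seen the site.

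Section 7.1 adds: "Reminders will be sent to parents between the four time points regarding looking at the website and the upcoming data collection calls". It also says: "We will also use a website plug-in to track any analyze how parents move through the website".

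Section 11.0 withdraws a parent whose T2 data cannot be collected before the visit. Failure to view the site is not among its reasons. Section 12.0 gives general descriptive statistics and sets no denominator or analysis set for acceptability.

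**The concern.** The acceptability items (Section 17.0) ask about amount of content, clarity, helpfulness, format and balance. Only someone who has seen the aid can answer them. By asking whether parents had time to look, the calendar allows for some who had not by T2. Those parents remain enrolled and may open the site later, but the schedule offers them no further chance to rate it.

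The primary acceptability result would then rest on parents who viewed promptly. Late viewers may differ from them, for example in available time, internet access or interest, and a pilot of implementation needs to hear from them. At T3, PrepDM scores and the answer on use of the aid would come from a group whose exposure at that moment was not asked. A larger trial planned from these data would inherit the gap.

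**Working it through.** The plan states no viewing rate, acceptability target or acceptability proportion, so there is no figure to reproduce. The main check is of the schedule.

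**Step 1. What is asked, and when (Section 8.0)**

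| Item | T1 | T2 | T3 | T4 |
|---|---|---|---|---|
| Website viewed (3 questions) | – | yes | – | – |
| Acceptability (4 questions) | – | yes | – | – |
| PrepDM (10 questions) | – | yes | yes | – |
| Use of the aid at the visit (open-ended) | – | – | yes | – |

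**Step 2. Follow a parent who has not viewed at T2 and opens the site before the visit**

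- T2: recorded as not having viewed. Whether the acceptability and PrepDM items are then asked is not stated. If they are, the answers are uninformed.
- After T2: stays in the study, because Section 11.0 does not list non-viewing. On the natural reading of Section 7.1, may receive a further reminder about the site.
- T3: answers PrepDM and the question on use of the aid. Is not asked about viewing or acceptability.
- T4: answers the regret scale and two open-ended questions. Neither viewing nor acceptability is asked.

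This parent has seen the aid and never gives a usable acceptability rating. That follows from the calendar whether or not T2 uses a skip rule.

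**Step 3. Possible size (illustration only)**

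Assumptions, none of them from the plan: 25 parents reach T2 (the top of the 10-25 range in Section 7.1), 20% have not viewed, acceptability is scored yes or no, and about 80% of viewers say yes.

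- Not viewed at T2: 0.20 × 25 = 5. Viewers: 25 − 5 = 20. Rated acceptable: 0.80 × 20 = 16.
- Acceptability among T2 viewers: 16/20 = 80% (exact 95% interval 56% to 94%).

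Let k of the 5 view before the visit. The unrated share of eventual viewers is k/(20 + k). The proportion acceptable among all eventual viewers could lie anywhere from 16/(20 + k) to (16 + k)/(20 + k).

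| k | Unrated share | Lowest | Highest |
|---|---|---|---|
| 0 | 0/20 = 0% | 16/20 = 80% | 16/20 = 80% |
| 2 | 2/22 = 9% | 16/22 = 73% | 18/22 = 82% |
| 5 | 5/25 = 20% | 16/25 = 64% | 21/25 = 84% |

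**Step 4. The unstated T2 denominator**

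This matters only if non-viewers are asked or counted. The columns show the result with non-viewers excluded, all counted as no, and all counted as yes.

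| Parents | Not viewed | Excluded | All no | All yes |
|---|---|---|---|---|
| 25 | 2 (about 10%) | 18/23 = 78% | 18/25 = 72% | 20/25 = 80% |
| 25 | 5 (20%) | 16/20 = 80% | 16/25 = 64% | 21/25 = 84% |
| 25 | 8 (about 30%) | 14/17 = 82% | 14/25 = 56% | 22/25 = 88% |
| 40 | 8 (20%) | 26/32 = 81% | 26/40 = 65% | 34/40 = 85% |

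The shift can go either way and depends on a viewing rate that the plan does not give.

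**The case against.** A reader might infer that non-viewers are asked the acceptability items at T2 and that their answers enter the primary result. The documents do not support that. The calendar lists instruments and is not an interview script. It shows no branching even for the questions on who else was present and which device was used, which make sense only for viewers. The viewing question is listed first, a research assistant conducts the call, and Section 14.0 lets participants skip any question. Because viewing is recorded on the same call, a viewer-only result can be computed from the scheduled T2 data. This part of the objection stands: at T2, what is missing is a stated skip rule and denominator.

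A reader might also infer that T3 scores cannot be related to exposure at all. That goes too far. The T2 items, the plug-in and the T3 use question all bear on exposure, and Section 12.0 plans no sub-analyses. However, linkage of plug-in records to individual parents is not stated, and the plug-in yields no ratings. The T3 use question covers the visit only, and Section 12.0 classes qualitative results as exploratory. None of these supplies a late viewer's acceptability rating.

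The reminder sentence covers two subjects, and could mean website reminders before T2 and call reminders afterwards. Reminders in every interval is the more natural reading. The gap does not depend on it, since a parent may open the site unprompted.

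Finally, a rating taken before the consultation is free of the urologist's influence. That is a good reason to keep T2 as the main time point and to show later ratings apart. It is not a reason to forgo them.

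**Conclusion.** The point holds as a gap in the schedule. Under the calendar as written, the primary acceptability result can draw usable ratings only from parents who had viewed by T2. Parents who first view between T2 and the visit are never asked once they have seen the aid, and the T3 questions about the aid have no exposure item beside them. The T2 skip rule and denominator are unstated, which is missing detail rather than evidence that non-viewers are counted.

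The size is unknown. It depends on the share who have not viewed by T2 and on the time from T2 to the visit, and the documents give neither. If every parent views within the first week, or T2 falls just before the visit, there is no loss. In the illustration, 0% to 20% of eventual viewers go unrated. No stated decision threshold turns on the result. The change is worth making because it is cheap and the outcome is primary.

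**What to change.** In Section 8.0, at T3:

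- repeat the three website-viewing items;
- give the four-item acceptability questionnaire to parents who had not viewed by T2 but have since.

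In Sections 8.0 and 12.0:

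- state whether the T2 acceptability and PrepDM items are asked only of parents who have viewed;
- report acceptability among viewers, with pre-consultation (T2) and post-consultation (T3) ratings shown separately;
- give beside them the numbers who viewed by T2, by T3 and never.

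Cost: T3 now has 2 + 16 + 9 + 10 + 3 = 40 questions. It would have 40 + 3 = 43 for most parents and 43 + 4 = 47 for late viewers, on a call that already takes place. Late ratings may be coloured by the consultation and may come from only a handful of parents, so they should be described and not pooled with the T2 ratings.
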